### 5.3 Procedures for Handling Missing Data and Outliers

Every effort will be made to collect all the data and avoid missing data. For intention—to-treat (ITT) efficacy data, multiple sensitivity analyses will be completed. Further details about sensitivity analyses can be found in Section 6.2.1.6.

All missing values will be queried and resolved to the best possible extent. Unless specifically noted otherwise, missing values will not be imputed.

### **5.4 Interim Analysis**

An interim analysis will not be performed.

#### 5.5 Blinded Review of Data

The checking and assessment of data to revisit the proposed methods of statistical analysis for the purpose of finalizing the planned analysis prior to the breaking of the blind will be conducted by

The following lists some of the aspects of the blinded data review that would be considered:

- Checking of data for important/not important protocol deviations;
- Precise determination of analysis populations (intent-to-treat, per-protocol, and safety), especially which subjects will be included and which will be excluded from these populations;
- Handling of missing data;
- Outlier identification in the data and specific decisions taken on how these will be handled;
- Reviewing and identifying concomitantly used medications that have potential antispasticity or neurological effects;
- Reviewing and identifying changes in physiotherapy regimens;
- Reviewing and identifying adverse events for potential confounding of modified Ashworth scores.

The blinded data review will be discussed with SPARC Ltd. and will be documented in agreed and signed meeting minutes.

### 5.6 Final Reporting and Analysis

The randomization code will be broken at the end of the trial when all subjects have completed the study and only after all data have been entered into the database, cleaned, antispasticity medication use identified, and the database locked. Prior to the final unblinding, a review to identify the Per Protocol population will be undertaken. After database lock, the results will be analyzed and unblinded to the CRO statistician, programmer, and Sponsor.

All analyses outlined in the protocol and in this SAP will be carried out after:

- The SAP has been approved;
- The study database has been authorized by the study clinical team as complete and final;
- All analysis populations are determined;
- Treatment Failures have been identified; and
- Protocol deviations have been identified.

Further exploratory analyses not necessarily identified in this SAP may be performed to support the clinical development program. Any post hoc or unplanned analyses performed and not identified in this SAP will be clearly identified in the CSR.

#### 5.7 Multi-center Studies

There are expected to be approximately 75 study sites in this study. Due to the large number of study sites and the small numbers of subjects per site, the analysis of efficacy endpoints will not include adjustments for study site.

#### 6. STATISTICAL ANALYSIS METHODOLOGY

All data collected for this study will be presented in summary tables, figures, and listings (TFLs) as indicated in Appendix 1 of this SAP. Shells for TFLs with enough detail for programming will be provided as a guide to develop the programming SAS codes. These shells will be in sufficient detail to simulate the actual TFLs when they are created from the locked database.

Appropriate descriptive statistics will be computed and displayed (by time point and other key variables as appropriate) for both continuous and categorical variables. For continuous variables, descriptive statistics will include n (the number of subjects with non-missing data), mean, standard deviation (SD), median, 95% confidence interval, minimum and maximum values. For categorical data, the number and percentage of subjects within each category will be presented. The denominator for percentages will be based on the number of subjects with non-missing data appropriate for summary purposes. Unless otherwise noted, all percentages will be presented to one decimal place.

Individual data listings of all data represented on the eCRF and from the clinical laboratory will be presented.

### 6.1 Study Subjects

### 6.1.1 Subject Disposition

The final study disposition of each subject will be captured in the eCRF. For those subjects who do not complete the study as planned, all potential reasons for discontinuation should be provided, with one indicated as primary. The reasons for discontinuation will be categorized as described below and the following descriptive summaries of study disposition will be provided.

- Number of subjects who were enrolled in each phase of the study (Part 1, Part 2, Part 3):
  - o Part 1: Received at Visit 1
  - o Part 2: Received at Visit 2 (Safety Population)
  - o Part 3:
    - Randomized at Visit 7
    - Dispensed Blinded Study Drug at Visit 7 (Safety Population Part 3) by treatment group and overall
    - Intent-to-Treat Population by treatment group and overall
    - Per Protocol Population by treatment group and overall
- Number and proportion of subjects (overall for Parts 1 and 2 and by treatment group and overall for Part 3) who discontinued each phase of the study.
- Number and proportion of subjects (overall for Parts 1 and 2 and by treatment group and overall for Part3) who dropped-out for each of the following categories (based on primary reason and also based on all reasons) for why a subject may be prematurely discontinued from the study.

- Withdrew Consent
- Adverse Event
- MS-related Disease Progression

0

- Required Dose Change Between Visit 4 and Visit 11
- Major Protocol Deviation
- Lost to Follow-up
- Worsening of Clinical Condition or Loss of Efficacy
- o Withdrew, Per Sponsor
- o Withdrew, Per Investigator
- Other

A listing of subject disposition will be prepared, inclusive of dates of last dose and last contact, and any investigator comments regarding reason for discontinuation. A summary table will tabulate overall disposition of the subjects by the categories above. A CONSORT figure will summarize subject disposition.

### 6.1.2 **Demographics**

Descriptive summaries of the Safety Population will be prepared for the demographic and baseline (Screening) parameters listed below. Categorical variables will be described with counts and percentages and continuous variables with mean and 95% confidence interval (CI). These variables will also be summarized for the ITT population (and also for the PP population if it differs from the ITT population by more than 10% in overall sample size).

- Age (years)
- Age Group (<65 vs. ≥65)
- Gender
- Race/ethnicity

•

- Height (cm)
- Weight (kg)
- BMI ( $kg/m^2$ )

•

#### **6.1.3 Protocol Deviations**

A protocol deviation is any change, divergence, or departure from the study design or procedure defined in the protocol.

21Sep2017

A subset of the protocol deviations can be identified as an important protocol deviation as described below:

Important Protocol Deviation: A protocol deviation that might significantly affect the completeness, accuracy, and/or reliability of the study data or that might significantly affect a subject's rights, safety, or well-being. Important deviations include includion/exclusion criteria violations, cases where withdrawal criteria developed but the subject was not withdrawn, receiving the wrong treatment or incorrect dose, and receiving excluded concomitant medications.

Upon soft lock of the database, all documented protocol deviations in the study will be reviewed to identify all important protocol deviations by a data review team including representatives from clinical operations, medical, data management, and statistics, and sent to the sponsor for approval. Final decisions will be documented and databased.

Protocol violations during Part 3 will be summarized by treatment group for the ITT population, and all protocol violations and deviations will be listed.

### 6.1.4 Medical and Surgical History

Medical history at Visit 1 (prior conditions and present conditions) will be coded using version 15.0 of the Medical Dictionary for Regulatory Activities (MedDRA®) and tabulated by system organ class and preferred term. A by subject listing will also be created.

### 6.1.5 Multiple Sclerosis History

Multiple sclerosis history at screening will be summarized by MS type, MS duration (years), course severity, symptoms/signs symmetrical, time since last relapse (months), for the ITT and Safety Populations. This information will also be presented in a data listing.

#### 6.1.6 **Spasticity History**

Spasticity history at Screening will be summarized by duration of spasticity (years), daily frequency before treatment,

for the ITT and Safety Populations. This information will also be presented in a data listing.

#### 6.1.7 Concomitant Medications

Prior and concomitant medications will be coded using the most current version available of the World Health Organization Drug Dictionary (WHODRUG) March 2012. These will be summarized based on Anatomical Therapeutic Chemical (ATC) classification level 3 and Preferred Name, using incidence and percentage.

Neurological and anti- spasticity concomitant medications, identified during blinded data review, will be summarized separately overall for Part 2 and by treatment group and overall for Part 3 using counts and percentages and will be listed for all subjects.

Medications used only during Screening and/or the run-in treatment (i.e., discontinued prior to the first dose of will be considered Prior Medications. These will be summarized separately.

A Concomitant Medication is defined as a medication that was started prior to the first dose of and that continued for at least 1 day following the start of or that was started after the start of

Concomitant medications will be summarized separately for Parts 2 and 3. Concomitant status will be re-confirmed for Part 3.

When medication start and/or stop dates are missing, the following imputations will be made (subject to medical review):

- Missing Medication Start Dates
  - 1. If onset date is completely missing, then onset date is set to date of first dose
  - 2. If year is present and (month and day are missing), or (month is missing but day is present):
    - a. If year = year of first dose, then set date to first dose date
    - b. If year < year of first dose and medication stop month and year are available, then set to first of the end month
    - c. Otherwise if year < year of first dose, then set month and day to December 31st.
    - d. If year > year of first dose, then set month and day to January 1st.
  - 3. If month and year are present and day is missing:
    - a. If year=year of first dose and
      - i. If month = month of first dose then set day to day of first dose date
      - ii. If month < month of first dose then set day to last day of month
      - iii. If month > month of first dose then set day to first day of month
    - b. If year < year of first dose then set day to last day of month
    - c. If year > year of first dose then set day to first day of month
  - 4. If the medication start date is completely missing and the corresponding stop date is completely missing, the medication start date will remain missing.
- Missing Medication Stop Dates

[figure not shown]
If the stop date is completely missing, the stop day will not be estimated (i.e., the medication will be assumed to be continuing).

If only the day of Medication stop is unknown, the day will be assumed to the last of the month (e.g. ??-JAN-2011 will be treated as 31-JAN-2011).

A by-subject listing comprehensive of prior and concomitant medications will be generated, inclusive of verbatim and coded terms, doses and routes, and start and stop dates. Prior medications will be flagged. Prior and concomitant status with respect to study drug treatment will be determined based on imputed dates as defined above. Prior medications used within 30 days of Screening will be provided in a separate listing.

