#### 10.4.5.1 Adverse Events

All treatment-emergent adverse events (TEAE) will be coded in a standardized manner for regulatory activities. TEAEs will be coded according to body systems and preferred terms. A

Confidential Page 59 of 67

 
TEAE is defined as any event that only occurred after administration or that existed before drug administration but increased in severity or treatment attribution. For the randomized withdrawal phase, emergent events will be determined relative to the double-blind medication.
Adverse events reported as pre-existing at the start of the run-in or that emerge during the treatment phase will be considered pre-treatment adverse events. These will be summarized separately.
The incidence of TEAEs and SAEs will be summarized for the s (Part 2) and also by treatment group during the double-blind, par (Part 3). For each part, the incidence of TEAEs will be presented by system organ classification and preferred terms according to the Medical Dictionary for Regulatory Activities (MedDRA®), by causality, by severity, and by action taken. In addition, separate summaries will be prepared with subjects categorized by sex, age (below 65 years of age and 65 years of age and older), and race.
The effects of concomitant medications and/or medical conditions present at screening will also be explored. Should any medications be used by or conditions be present in 20% or more of the subjects overall, subjects will be categorized accordingly and the incidence of TEAEs in each par summarized. Additional drugs or diagnoses of interest may be identified during the blinded data review.
In addition, adverse events will be listed for all subjects, including verbatim and coded terms.
10.4.5.2

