#### **Subgroup Analyses** 6.2.4.6

## **6.3 Safety Analysis**

#### 6.3.1 Adverse Events

All adverse events will be coded using version 15.0 of MedDRA, which will be noted in the CSR.

Adverse events reported as pre-existing at the start of the run-in emerge during the treatment phase will be considered pre-treatment adverse events; these will be flagged in a listing.

A treatment-emergent adverse experience (TEAE) is defined as any event that only occurred after administration or that existed before drug administration but increased in severity or treatment attribution.

The duration of an AE will be calculated as:

$$Duration = (AE End Date - AE Onset Date) + 1$$

When AE start and/or stop dates are missing, the following imputations will be made (subject to medical review):

- Missing AE Start Dates
- 1. If onset date is completely missing, then onset date is set to date of first dose
- 2. If year is present and (month and day are missing), or (month is missing but day is present):
  - a. If year = year of first dose, then set date to first dose date
  - b. If year < year of first dose and medication stop month and year are available, then set to first of the end month
  - c. Otherwise if year < year of first dose, then set month and day to December 31st.
  - d. If year > year of first dose, then set month and day to January 1st.
- 3. If month and year are present and day is missing:
  - a. If year=year of first dose and

- i. If month = month of first dose then set day to day of first dose date
- ii. If month < month of first dose then set day to last day of month
- iii. If month > month of first dose then set day to first day of month
- b. If year < year of first dose then set day to last day of month
- c. If year > year of first dose then set day to first day of month
- 4. If the AE start date is completely missing and the corresponding stop date is completely missing, the AE start date will remain missing.

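### Partial-date rule 2b in SAP 6.1.7 and 6.3.1 overwrites a recorded earlier start year with the stop month, even when the stop falls in a later year (minor)

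*SAP*

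**What the plan says.** SAP 6.1.7 gives a ladder of rules for incomplete medication start dates. For a start with a known year but no month, where that year is before the first-dose year, rule 2b reads: "If year < year of first dose and medication stop month and year are available, then set to first of the end month". If the stop month and year are not available, rule 2c applies: "Otherwise if year < year of first dose, then set month and day to December 31st". When month and year are both known and only the day is missing, rule 3b reads: "If year < year of first dose then set day to last day of month".

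The same section then says: "Prior and concomitant status with respect to study drug treatment will be determined based on imputed dates as defined above". It qualifies the ladder with: "the following imputations will be made (subject to medical review").

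SAP 6.3.1 uses the same ladder for AE onset and keeps the medication wording: "b. If year < year of first dose and medication stop month and year are available, then set to first of the end month". A TEAE is "defined as any event that only occurred after administration or that existed before drug administration" and then worsened. For Part 3, Protocol 10.4.5.1 adds: "For the randomized withdrawal phase, emergent events will be determined relative to the double-blind medication".

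**The concern.** The recorded year is information, and rules 2c and 3b respect it. Rule 2b discards it when the stop date is better documented, so knowing more about the end of a record gives a worse estimate of its beginning. The rule is sensible in one case: when start and stop fall in the same year, it prevents 2c from placing the start after the stop. That condition is not written.

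What depends on the start date is:
- which drugs appear in the Part 2 concomitant summary;
- the listing of drugs used within 30 days of Screening;
- for AEs, the duration, the dose at onset and the treatment-emergent classification.

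The reference to a medication stop date in 6.3.1 also leaves the programmer unsure what the AE rule tests.

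**Working it through.** **Inputs.** The rules are as in SAP 6.1.7. Part 2 runs from Visit 2 (Day 8) to Visit 7 (Day 120), 120 − 8 = 112 days. Part 3 runs to Visit 11 (Day 148), 148 − 120 = 28 days. The plan states no figure for this point, so there is none to reproduce. Assumptions: first dose means the start of Part 2 (the product name is missing from the text), and stop dates are uniform over days 0 to 140 after first dose.

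**The rule applied literally** (illustrative record: start year 2009, first dose 16-Jun-2014, Visit 7 on 06-Oct-2014):
- Stop 20-Aug-2014: 2b gives 01-Aug-2014, on study and about 4.6 years after the latest date that the recorded year allows.
- Stop 25-Jun-2014: 2b gives 01-Jun-2014. The year is wrong, but the start is still before first dose.
- Stop 25-Oct-2014, in Part 3: 2b gives 01-Oct-2014, still before Visit 7, so the drug stays in the Part 2 summary. With this first-dose date, only a Part 3 stop on 1 to 3 November gives a start after Visit 7.
- Ongoing: 2c gives 31-Dec-2009, the correct year.

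**How often the imputed start falls after a milestone.** The start falls before the milestone only if the stop lies in the milestone's own calendar month and the milestone is not the 1st. Averaged over four calendar years of milestone dates, about 14.7 days of the stop window meet that condition.
- First dose, 141 possible stop days: 1 − 14.7/141 = 89.6% get a start on or after first dose.
- Visit 7, 29 possible stop days (112 to 140): 1 − 14.7/29 = 49.3% get a start on or after Visit 7.
- As a share of all affected drugs stopped on study: 29/141 × 49.3% = 10.1%.

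A full enumeration of 1,461 first-dose dates × 141 stop days = 206,001 cases gives the same 89.6% and 49.3%.

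**Prior/concomitant status.** Status depends on use after first dose, which the stop date settles. It changes only when first dose falls on the 1st of a month and the stop is that same day: 48/206,001 = 0.02%.

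**Listing of use within 30 days of Screening.** A drug whose imputed start falls after Screening no longer appears to have been in use before it, and can be lost from the listing.

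**AE duration.** SAP 6.3.1 computes end minus onset plus 1. If onset is the first of the end month, the maximum is 31 − 1 + 1 = 31 days, however long the event lasted.

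**After the change proposed below.** None of the enumerated records gets an on-study start. A record starting in 2013 and stopping 10-Mar-2013 still gets 01-Mar-2013, so the start does not pass the stop.

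**The case against.** Most of the case against goes to consequences, and much of it stands.

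- A reader might infer that about 90% of affected medications are misclassified. They are not. That figure describes where the imputed date lands, while status moves in 0.02% of cases.
- A reader might infer that the Part 3 medication table is distorted. A drug stopped in Part 3 was used in Part 3 whatever its start, and the table reports incidence by class and name, not new starts.
- A reader might infer a wave of false TEAEs. Pre-study conditions go to medical history at Visit 1, and events reported as pre-existing at the start of the run-in are classed as pre-treatment. AE collection starts at Screening, at most 14 days before Visit 1, and Visit 2 is 7 days later. A newly collected AE with an onset year before the first-dose year therefore needs a first dose in about the first three weeks of January. The sentence tying status to imputed dates covers medications only.
- A reader might infer harm to the blinded review of confounding drugs. Nothing says that its members see only imputed dates.

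Two defences are weaker. Rule 2b could be read as borrowing only the stop month and keeping the recorded year. But it requires the stop year to be available and sets the whole date, whereas 2c and 2d set only month and day. If that reading was intended, the sentence still needs correcting. Medical review may catch individual records, but no criterion or replacement rule is given.

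**Conclusion.** The rule is wrong as written, and the consequences are minor. It affects only records with a year-only start in an earlier year and a known stop month and year. Within that set, about half of the drugs stopped in Part 3, or roughly 10% of those stopped on study, would be lost from the Part 2 concomitant summary, and some drugs could be lost from the 30-day listing. For AEs, the rule caps computed duration at 31 days and can produce a false TEAE with a wrong dose at onset. In Part 3 such a TEAE could enter the tables by treatment group, but these cases should be few.

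The percentages rest on uniform stop dates and on first dose being the start of Part 2. The number of affected records cannot be known from the documents. The primary endpoint uses CGIC and modified Ashworth scores, not these dates, and is not affected.

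**What to change.** In SAP 6.1.7 and 6.3.1, limit rule 2b to records whose stop year equals the recorded start year. Otherwise apply rule 2c, 31 December of the recorded year, which always precedes a stop in a later year. In 6.3.1, replace the reference to the medication stop date with the AE stop date. The cost is one sentence in each of two sections and a small programming change, with no effect on data collection or trial conduct.

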### 6.1.8 Exposure and Compliance

Exposure data at each visit starting with Visit 1 will be summarized for the Safety Population for Parts 1 and 2, and for Part 3, separately. Specifically, the numbers of subjects for each dose level will be summarized with counts and percentages, and descriptive summaries (mean, 95% confidence interval, median, mode, and standard deviation) of dose at each visit will be provided. The number of tablets of exposure will be calculated for each visit and will also be summarized, where the exposure is calculated as (number of tablets dispensed – number of tablets returned). Exposure duration for each visit will also be summaried, where duration is calculated as ((last dose date – first dose date) + 1). For Safety Population Part 3, summaries will be included of down-titration exposure in the placebo randomized group.

Study medication will be dispensed by the site personnel with the amount dispensed and the amount returned documented in the eCRF. Treatment compliance will be calculated using the number of capsules dispensed minus the number of capsules returned, divided by the number of capsules intended to be taken. Average compliance will be summarized descriptively by visit, and for the study overall. A further categorical summary of compliance will be provided by visit, and for the study overall, using the following categories: <75%,  $\ge75\%$  to  $\le125\%$ , and >125%.

Individual subject listings of dosing will be prepared, based on dispense dates and subject diary data. A separate listing of drug accountability will be prepared.

